The current population of type 2 diabetes mellitus worldwide is over 200 million and Malaysia contributes to 1.2% of that number¹. Type 2 diabetes mellitus is a progressive disease associated with debilitating microvascular and macrovascular complications. The prevalence of T2DM in Malaysia has approximately tripled over the last three decades from 6.3% in 1986 to 17.5% of the adult population in 2015². The prevalence of chronic kidney disease (CKD) in Peninsular Malaysia was high at 9.1% of the adult population in 2011. Among these, 4.2% patients were in CKD stage 1, 2.0% in CKD stage 2, 2.3% in CKD stage 3, 0.2% in CKD stage 4, and 0.4% in CKD stage 5³. Diabetes is the leading cause of renal failure for patients commencing dialysis, increasing from 53% of new dialysis patients in 2004 to 61% in 2013⁴. Therefore, diabetic kidney disease (DKD) is a debilitating complication which not only imposes significant health problems but also confers financial burden on affected patients. There has been increasing amount of understanding in the complexity of the relationship between T2DM and obesity. As the prevalence of both conditions continue to demonstrate a parallel rise, the influence of obesity on T2DM is further marked. Thus, this has led to greater emphasis on weight loss in the management of T2DM. More recent anti-diabetic medications including SGLT-2 inhibitors and GLP1 agonists demonstrated greater efficacy in improving glycaemic control and their ability to produce weight reduction. In addition, there has been more interest in the effects of these drugs on retardation of renal disease progression. The mechanism is unclear, either attributed by direct drug effects on renal glomerular-tubular structures, through the Renin-Angiotensin-Aldosterone-System (RAAS), or other pathways. Another plausible explanation is the significant weight loss, which has been shown to have a significant effect of attenuation of renal disease.

Weight reduction programs have long been a complex and tedious treatment plan which has inconsistent, non-duplicable and unpredictable outcomes. Most programs

emphasized on medical nutrition therapy and lifestyle changes. There have been many different dietary plans which share a common goal ie to reduce calorie intake whilst increasing energy expenditure. Few have been successfully reproducible, limited by either patient adherence or modest outcome.

Low carbohydrate diet is a diet plan which stresses on reducing carbohydrate intake to less than 20g daily. Numerous studies have shown that weight loss could be obtained by reduction of calorie intake in either the form of carbohydrate or fat. CKD patients are recommended to consume low protein diet of less than 0.6-0.7g/kg/day with little emphasis on calorie or carbohydrate intake.

This study, thus, aims to evaluate the effects of low carbohydrate and moderate fat (LCBD) in addition to low protein diet on renal disease in patients with DKD.

Objectives

1. To evaluate the effects of LCBD in comparison to low protein diet (LPD) alone on renal outcome in patients with DKD
2. To evaluate the effects of LCBD in comparison to low protein diet (LPD) alone on anthropometric and other metabolic parameters in patients with DKD
3. To determine the associations between renal outcome and metabolic parameters in patients with DKD who received LCBD and standard therapy.

OUTCOME MEASURES

Primary Outcome

1. Proteinuria as assessed by UACR
2. Rise in serum creatinine, reduction in eGFR

Secondary Outcomes

- 1. Weight loss, blood pressure**
- 2. Metabolic parameters- lipid profile and inflammatory markers including hsCRP, IL-6**

HYPOTHESES

LCBD reduces proteinuria and improves renal function compared to standard treatment in patients with DKD.

LCBD causes significant weight loss and improvement in other metabolic parameters compared to standard treatment in patients with DKD.

Study Design

This is an investigator-initiated, single centre, randomized, controlled, clinical trial in Type 2 diabetes mellitus patients, comparing 12-weeks of LCBD compared to standard medical therapy in patients with DKD.

Patient Selection

Recruitment would be conducted at the Endocrinology and Nephrology clinics of UiTM. Patients with Type 2 Diabetes Mellitus undergoing follow-up in these clinics who meet the inclusion and exclusion criteria will be invited to participate in the study.

Inclusion Criteria

1. Diagnosed with Type 2 DM of more than 5 years
2. Diagnosis of stable CKD of more than 6 months
3. HbA1c of 7% - 10.5%
4. Patient age between 40-75 years old
5. Able to sign informed consent

Exclusion Criteria

1. Type 1 DM
2. Frequent hypoglycemia
3. Persistent elevations of serum liver transminase
4. Heart failure (New York Heart Association functional class III-IV), active systemic inflammatory disease, chronic renal failure requiring hemodialysis, active hepatic disease and collagen disease
5. Malignancy
6. Recent hospital admission for acute within the past 3 months
7. Pregnant women, breastfeeding or planning to conceive within the next year

All patients who fulfilled the inclusion and exclusion criteria will be offered to participate in the study and written consent will be obtained.

SAMPLE SIZE CALCULATION

This is a single centre, interventional, randomised, controlled clinical trial. This will be a pilot study involving 20 patients per arm. However, considering a **20% dropout, we would be recruiting 24 patients per arm.**

STATISTICAL ANALYSIS

The SPSS program will be used for the statistical analysis. Differences between before and after intervention will be analyzed by employing one-way ANOVA, following unpaired t-test. A Pearson's correlation analysis would be carried out to determine the correlation of the changes of proteinuria, creatinine, weight loss, and other variables. levels and surrogate endothelial function marker.

STUDY PROTOCOL

Following informed consent, patients would be randomised to either LCBD or low protein Diet (LPD) group.

All recruited patients will be given the standard dietary and exercise advice which will include low protein of 0.6-0.7g/kg/day and low salt diet.

In addition, patients within the LCBD will be given a prescription diet of 20g of carbohydrate daily. This will be supplemented by visual aids on carbohydrate counts of various local food. Patients would be given the option to choose their most appropriate food types which will amount to the carbohydrate count given. Patients on oral anti-diabetic treatment including insulin will be advised on titrations of their medications to avoid hypoglycaemia.

The control arm will not be given any additional advice.

All patients will be required to fill in a 3day food diary during their scheduled visits which will be at 6 weeks and 12 weeks.

Clinical assessments include blood sampling which will be done at baseline and at study end.

ULTRASOUND FOR FATTY LIVER

Ultrasound is widely used as a first-line investigation for hepatic steatosis. It provides a qualitative assessment of fatty infiltration of the liver. Grading of diffuse hepatic steatosis can demonstrate the extent of fatty changes in the liver. A senior consultant radiologist who has previous experience in such studies will perform abdominal ultrasound. Each case will be graded as normal, mild fatty liver, moderate fatty liver or severe fatty liver. The liver will be assessed to be normal if the texture is homogeneous, exhibits fine-level echoes, or is minimally hyperechoic or isoechoic compared with normal renal cortex and if there is no posterior attenuation of the ultrasound beam. Mild steatosis is seen as a slight increase in liver echogenicity. In moderate steatosis, visualization of intrahepatic vessels and the diaphragm is slightly impaired, and increased liver echogenicity is present. Severe steatosis is recognized as a marked increase in hepatic echogenicity, poor penetration of the posterior segment of the right lobe of the liver, and poor or no visualization of the hepatic vessels and diaphragm⁵.

Dual energy x-ray absorptiometry (DEXA) SCAN⁶

[figure not shown]
Dual energy x-ray absorptiometry (DEXA) was once used for determining bone density however it has now evolved into a technique for also estimating body composition. DEXA can measure bone mineral content (BMC), bone mineral density (BMD), fat-free mass (FFM), and can also provide estimates of percent body fat. It is widely regarded as one of the most proven and reliable technologies for measuring body composition. DEXA works by measuring the body's absorbance of x-rays at two different energies. Fat, bone mineral, and fat-free soft tissue have different absorption properties. The amount of radiation exposure during a DEXA scan varies based on the region of the body scanned and is much lower than standard plain radiography examinations. DEXA scan is less than two days' exposure to natural background radiation (NBR). In comparison, a plain radiograph of the chest is equivalent to approximately three days of exposure to NBR, and a transatlantic flight is approximately a week's exposure to NBR. Improved technology has dramatically decreased scan times to 5-10 minutes making this method convenient and non-invasive. DEXA allows accurate and comprehensive measurements of total body fat percentage, and also segmental body fat distribution in regions such as arms, legs, waist and hips. Another advantage of DEXA is it can measure the visceral fat content in the waist region. Visceral fat is of particular concern as it is a key player in many

preventable diseases. It is extremely valuable in research as it can be used to obtain an initial body composition assessment and to understand how body is changing over time, that is, how much lean and fat tissue changes over time therefore measuring the impact of training or dietary programs. The scan is a quick and painless procedure whereby the patient lies on the back of the DEXA table. No special preparation is needed before the scan. Analysis of the results is done by the DEXA computer software.

References:

2. National Health and Morbidity Survey 2015 (NHMS 2015). Ministry of Health, Kuala Lumpur, Malaysia(2015)
3. L.S. Hooi, L.M. Ong, G. Ahmad, *et al.* A population-based study measuring the prevalence of chronic kidney disease among adults in West Malaysia. *Kidney Int*, 84 (2013), pp. 1034-1040.
4. B. Goh, L. Ong, Y. LimTwenty First Report of the Malaysian Dialysis and Transplant 2013. Malaysian Society of Nephrology, Kuala Lumpur, Malaysia (2014)
6. Australian Radiation Protection and Nuclear Safety Agency. Ionizing Radiation and Health. Updated 3 December 2003. <https://www.legislation.gov.au/Details/F2019C00829>

FLOWCHART

Effects of Low Carbohydrate Diet (LCBD) on Weight and Renal Outcome in Patients with Diabetic Kidney Disease (DKD)- A pilot study
Revised Budget

No	Item	Price per item (RM)	Quantity	Total (RM)
1	Fasting plasma glucose	15	96	1,440
2	HbA1c	25	96	2,400
3	Lipid profile	15	96	1,440
4	Liver profile	15	96	1,440
5	Renal profile	15	96	1,440
6	UPCI	15	96	1,440
6	ELISA kits for surrogate markers hsCRP	2000/kit	2	4,000
7	ELISA kits for IL-6	3000/kit	2	6,000
8	Insulin (for 100 tests)	2,350	1	2,350
9	Glucometer and strips	200	48	9,600
10	Patient reimbursement	50/ visit	50 x 9 x 24 = 50 x 7 x 24	10,800 + 8,400 = 19,200
11	USS (Fatty liver)	50	96	4,800
12	Dexa	190	96	19,200
10	Stationery + Visual Aids	50/patient	48	2,400
			TOTAL	76,950

Gaant Chart

See Appendix A

Key Milestones

Milestone	Timeline	Milestone description
Ethics Approval	Sept 2018	Starting of recruitment
Patient Recruitment	Dec 2018	50% recruitment
	March 2019	100% recruitment
Patient randomisation	Dec 2018 Blood sampling and other measurements	50%
	April 2019	100% randomised
Data Compilation	Jul 2019	100% data compilation
Data Analysis and interpretation	Sept 2019	Completed data collection and performing Statistical analysis
Report Writing	Dec 2019	Completed report writing
Submission report	Feb 2020	Submission completed

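### Do the moderate-fat label on the LCBD arm and the lack of a stated food-diary analysis weaken the trial's comparison?

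*Combined protocol and SAP*

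**What the plan says.** The last sentence before the Objectives gives the aim as evaluating "low carbohydrate and moderate fat (LCBD) in addition to low protein diet on renal disease in patients with DKD". This is the only statement about the fat content of the trial diet. The Objectives, Hypotheses and Study Design use the abbreviation LCBD alone, and the project title near the end of the document expands it simply as a low carbohydrate diet.

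Under STUDY PROTOCOL, all patients receive standard advice that includes "low protein of 0.6-0.7g/kg/day and low salt diet". In addition, "patients within the LCBD will be given a prescription diet of 20g of carbohydrate daily", and these patients may "choose their most appropriate food types which will amount to the carbohydrate count given". No fat amount, fat share or energy target is given. The control arm gets nothing beyond the standard advice.

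Two background sentences word similar figures as ceilings: "Low carbohydrate diet is a diet plan which stresses on reducing carbohydrate intake to less than 20g daily", and patients with CKD are said to be advised a "low protein diet of less than 0.6-0.7g/kg/day with little emphasis on calorie or carbohydrate intake".

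On measurement, every patient completes a "3day food diary during their scheduled visits which will be at 6 weeks and 12 weeks". OUTCOME MEASURES lists UACR, creatinine and eGFR as primary, and weight, blood pressure, lipids and inflammatory markers as secondary. Dietary intake is not listed. STATISTICAL ANALYSIS names one-way ANOVA, an unpaired t-test and a Pearson correlation to "determine the correlation of the changes of proteinuria, creatinine, weight loss, and other variables". No dietary variable is named.

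**The concern.** Two things look wrong.

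First, a diet with very little carbohydrate and restricted protein has to draw most of its energy from fat, unless total energy is very low. Calling it moderate in fat seems to contradict its own components.

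Second, LCBD patients count carbohydrate only, and protein is advised rather than measured out. They could replace the lost carbohydrate with fat, with protein, or with nothing. An effect on UACR, creatinine or eGFR could then reflect carbohydrate restriction at equal protein, a change in protein intake, or lower total energy. Objective 1 sets LCBD against low protein diet alone, so a reader will want to know whether protein intake stayed similar in the two arms. The diaries could show this, but the plan does not say how they will be used, and the text lists no diary at baseline.

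At stake is what an observed effect can be attributed to, and how accurately the tested diet is described.

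**Working it through.** **Inputs.** From STUDY PROTOCOL: carbohydrate 20 g/day and protein 0.6-0.7 g/kg/day. From SAMPLE SIZE CALCULATION: 20 patients per arm analysed, 24 recruited. Assumed, because the documents give none of them: energy of 4, 4 and 9 kcal/g for carbohydrate, protein and fat; body weight 50-100 kg; total intake 1,000-2,000 kcal/day. The plan states no fat share, so there is no figure of its own to reproduce.

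**Step 1: energy not from fat.** Non-fat kcal = 20 × 4 + weight × (0.6 to 0.7) × 4.

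- 50 kg: 80 + 120 to 140 = 200-220
- 70 kg: 80 + 168 to 196 = 248-276
- 100 kg: 80 + 240 to 280 = 320-360

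**Step 2: fat share** = 1 − non-fat kcal / total kcal.

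| Weight | 1,000 kcal | 1,500 kcal | 2,000 kcal |
|---|---|---|---|
| 50 kg | 78-80% | 85-87% | 89-90% |
| 70 kg | 72-75% | 82-83% | 86-88% |
| 100 kg | 64-68% | 76-79% | 82-84% |

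**Step 3: when is fat half of energy or less?** Total kcal must be at most 2 × non-fat kcal: 496-552 at 70 kg and 640-720 at 100 kg. At an extreme of 120 kg, 0.7 g/kg and 800 kcal, non-fat energy is 80 + 336 = 416 kcal and the fat share is 48%. Over the ordinary range, then, fat dominates as a share of energy.

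**Step 4: does that prove a contradiction?** Only if moderate refers to a share of energy. In grams, at 800 kcal/day and 60-90 kg, fat would be (800 − 332)/9 = 52 g to (800 − 224)/9 = 64 g. The documents neither define the word nor exclude that reading, although they prescribe no such energy restriction. This is a mismatch of wording that the text cannot settle.

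**Step 5: what uses the label?** The arms are defined by the carbohydrate prescription and the shared advice. No eligibility rule, procedure, outcome or test refers to fat intake, so no planned result depends on the word.

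**Step 6: is the randomised comparison affected?** No. Any difference in protein or energy that arises because patients were given LCBD advice is part of the effect of that advice. It is a consequence of allocation and does not confound the comparison.

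**Step 7: what would a baseline diary add?** Randomisation already makes an unadjusted comparison of week 6 and week 12 intake valid, so the gain is precision only. With 20 per arm, 80% power and two-sided 5%, the detectable difference is 0.91 SD. Adjustment for baseline multiplies it by √(1 − r²), giving 0.87, 0.79 or 0.65 SD at assumed correlations of 0.3, 0.5 or 0.7. With an assumed SD of 0.2 g/kg/day for protein, the 95% half-width is t(0.975, 38) × 0.2 × √(2/20) = 0.128, which becomes 0.122, 0.111 or 0.091 after adjustment. The whole advised protein band is 0.7 − 0.6 = 0.1 g/kg/day wide. Even the best case gives an interval of about ±0.09, so it could not establish close similarity of protein intake.

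**The case for a change.** The strongest argument for a change is that it is cheap and suits a pilot. The diaries are already collected. The background itself names weight loss as a possible renal mechanism and patient adherence as a limit of dietary programmes, so a description of what was eaten would be among the most useful products for a later trial. A wording correction, 48 extra diaries (24 × 2) and a short descriptive analysis would cost little. The arithmetic on fat share is also robust: only an energy intake far below anything stated would reverse it.

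Much of this stands. The label fits its components poorly, and a table of intake by arm belongs in the report. But an analyst holding two diaries per patient would produce that table without a written instruction, and the unpaired comparison already planned would serve for it. The baseline diary is a new measurement for a comparison that the plan does not make, and its gain rests on an unknown correlation in self-reported data.

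The absence of a baseline diary is also less certain than it looks. The flowchart and Appendix A are not shown. The budget reimburses 9 visits for 24 patients and 7 visits for another 24, while the text dates the diary visits only at weeks 6 and 12. The visible visit schedule is therefore incomplete.

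**Conclusion.** No change to the plan follows. The aim and the STUDY PROTOCOL section describe the LCBD arm in terms that sit badly together: if the stated carbohydrate and protein figures are followed, fat would be 64-90% of energy, assuming 50-100 kg and 1,000-2,000 kcal/day. The sponsor must reconcile the two places, and nothing here says which of them is right. The slip is clerical, because the phrase occurs once, is undefined, and governs no procedure, endpoint or analysis.

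The unstated diary analysis is a gap that analysts fill sensibly, by reporting protein, fat, carbohydrate and energy by arm at weeks 6 and 12 as a description of the diet eaten. A baseline diary with adjustment is optional. It would narrow a descriptive interval from 0.13 to between 0.12 and 0.09 g/kg/day, given an SD of 0.2 and correlations of 0.3 to 0.7, all assumed. It would alter no planned estimate or test. The primary comparison of the two sets of dietary advice remains valid as randomised; only the explanation of mechanism is limited, which is acceptable in a pilot with 20 patients per arm.

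### The only sentence on the treatment effect names no arm, no baseline adjustment and no scale for UACR; it should specify a between-arm, baseline-adjusted analysis

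*Combined protocol and SAP*

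**What the plan says.** The treatment-effect analysis is one sentence in STATISTICAL ANALYSIS: "Differences between before and after intervention will be analyzed by employing one-way ANOVA, following unpaired t-test". The only other analysis planned there is a Pearson correlation, to examine "the correlation of the changes of proteinuria, creatinine, weight loss, and other variables". That describes association and is not a treatment contrast.

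The questions are all between arms:
- The first objective is "To evaluate the effects of LCBD in comparison to low protein diet (LPD) alone on renal outcome in patients with DKD".
- The first hypothesis is "LCBD reduces proteinuria and improves renal function compared to standard treatment in patients with DKD".
- The design is described as "comparing 12-weeks of LCBD compared to standard medical therapy in patients with DKD".

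Under OUTCOME MEASURES the first primary outcome is "Proteinuria as assessed by UACR", with no transformation, ratio or change metric. Serum creatinine and eGFR are also listed as primary. No baseline covariate is mentioned anywhere. SAMPLE SIZE CALCULATION describes a pilot with 20 patients per arm, and 24 recruited per arm to allow for 20% dropout.

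**The concern.** The sentence can be read in two ways.

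- **Between-arm reading.** Each patient's change is computed, and the changes are compared between LCBD and LPD by an unpaired test. This fits the objectives, the hypotheses, the design, the word unpaired, and the reference to changes in the next sentence.
- **Literal reading.** Values before the intervention are tested against values after it, by an unpaired test. This treats two measurements on the same patient as independent and leaves the control arm out of the comparison.

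Naming two tests does not settle the matter. With two groups, one-way ANOVA and the equal-variance t-test are the same test (F = t²), so the sentence does not say what each step is for.

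The contrast and the scale therefore stay open until the data are in hand. On the first reading some precision is lost. On the second, the analysis does not answer the between-arm objectives.

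**Working it through.** **Inputs from the documents.** Two arms; 20 evaluable per arm; follow-up of 12 weeks. The recruitment figure reproduces as 20 × 1.2 = 24 (dividing by 0.8 would give 25); the point does not depend on it.

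**Inputs assumed, because the documents give none.** Lognormal UACR with the same log-SD (σ) at both times; σ of 0.5, 1.0 or 1.5; correlation ρ between baseline and week 12 of 0.3 to 0.9; two-sided 5% tests; a true 30% fall in LCBD only, so the log effect is ln 0.7 = −0.357.

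**Step 1: validity of the between-arm reading.** In simulation (20,000 trials per cell, σ = 1.0) with no LCBD effect and the same fall of 0 to 50% in both arms, the false-positive rate is 4.7–5.3% for log change and 3.7–4.2% for raw change. Nothing is biased.

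**Step 2: precision of the between-arm reading, log scale.**
- Change score: SE = σ√[2(1−ρ) × 2/20].
- ANCOVA: SE = σ√[(1−ρ²) × (2/20) × (1+1/36)].
- Variance ratio, ANCOVA to change score: (1+ρ)/2 × (1+1/36).

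Worked case, σ = 1.0 and ρ = 0.8:
- Change score: SE = √(0.4 × 0.1) = 0.200, and 0.357/0.200 = 1.78, giving power of about 41%.
- ANCOVA: SE = √(0.36 × 0.1 × 1.028) = 0.192, and 0.357/0.192 = 1.85, giving power of about 44%.

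| ρ | 0.3 | 0.5 | 0.7 | 0.8 | 0.9 |
|---|---|---|---|---|---|
| Variance ratio | 0.668 | 0.771 | 0.874 | 0.925 | 0.976 |
| 95% CI width ratio (simulated) | 0.82 | 0.88 | 0.94 | 0.96 | 0.99 |

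**Step 3: power by scale and adjustment (simulated).**

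| σ | ρ | Log ANCOVA | Log change | Raw ANCOVA | Raw change |
|---|---|---|---|---|---|
| 1.0 | 0.8 | 44% | 41% | 26% | 20% |
| 0.5 | 0.8 | 95% | 93% | 90% | 79% |
| 0.5 | 0.3 | 62% | 46% | 57% | 35% |
| 1.5 | 0.8 | 23% | 22% | 9% | 7% |

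At σ = 0.5 and ρ = 0.3, adjustment adds 16 points on the log scale (62 − 46) and 22 on the raw scale (57 − 35). Scale adds 5 under ANCOVA (62 − 57) and 11 under change scores (46 − 35). At σ = 1.5 and ρ = 0.8 the order reverses: adjustment adds 1 to 2 points and scale adds 14 to 15.

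**Step 4: the literal reading.** An unpaired before/after test in LCBD inflates the standard error by 1/√(1−ρ): 1.20, 1.41, 1.83, 2.24 and 3.16 at ρ = 0.3, 0.5, 0.7, 0.8 and 0.9. On the log scale it detects the 30% fall in 16, 13, 8, 5 and 2% of trials at σ = 1.0, and in 61–72% at σ = 0.5 over the same range of ρ. At σ = 1.0 and ρ = 0.3 even a paired test within LCBD reaches only about 25%, and the valid between-arm log change test about 15%. There the low power comes mainly from the sample size and the assumed effect.

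**Step 5: a shared fall.** Suppose both arms fall equally, and a diet effect is inferred because the literal log test is significant in LCBD but not in LPD. At σ = 1.0 and ρ = 0.8 this happens in 0.6, 5, 18 and 23% of trials for shared falls of 20, 30, 40 and 50%. A between-arm test would wrongly favour LCBD in about 2.5%.

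**The case against.** The strongest reply is that the context already settles the meaning. Objectives, hypotheses and design are all between arms, an unpaired test fits two independent groups, and a change-score comparison is valid. This is also a pilot with no power target, so no stated figure is wrong. Most of this stands. The between-arm reading is the likelier one, and ANCOVA and the log scale improve on a valid test; they do not correct a biased one. But the plan states superiority hypotheses and names tests for them. A pilot's main product is an estimate with its precision, which needs a named contrast and a named scale.

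Several stronger readings are tempting and are not supported:
- **That the plan commits to within-arm tests.** It does not; the sentence is ambiguous.
- **That scale always matters more than adjustment, or that the lack of adjustment costs little.** The rows at log-SD 0.5 contradict both.
- **That the literal test would miss most real effects.** This holds at log-SD 1.0 but not at 0.5.
- **That a shared fall would be credited to LCBD.** The documents nowhere state the rule in Step 5, and at correlation 0.8 the error is frequent only when the shared fall is large. Nothing in the documents predicts a large one: entry requires "Diagnosis of stable CKD of more than 6 months", and the advice common to both arms is described as standard: "All recruited patients will be given the standard dietary and exercise advice which will include low protein of 0.6-0.7g/kg/day and low salt diet".

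**Conclusion.** The point holds as a gap in specification and is worth fixing. That the sentence names no arm, covariate or UACR scale is certain from the text. On the likelier reading the cost is precision, not bias. At ρ from 0.3 to 0.9, ANCOVA narrows the 95% CI on the log scale by about 18% down to 1%. The spread in power from raw change to log ANCOVA is 20% to 44% at log-SD 1.0, ρ = 0.8, and 35% to 62% at log-SD 0.5, ρ = 0.3. Adjustment matters more at low correlation and low log-SD, and scale matters more at high log-SD. On the literal reading the analysis would not address the between-arm objectives at all, whatever its power.

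Confidence is high for the textual gap and lower for the sizes. Those rest on an assumed lognormal distribution, log-SD, correlation, 30% effect and two-sided 5% level, none of which the documents give.

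**What to change.** Replace the sentence with wording such as:

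> For each continuous outcome, including each listed primary outcome (UACR, serum creatinine, eGFR), LCBD is compared with LPD at week 12 by ANCOVA, with the week-12 value as outcome, arm as factor and the baseline value as covariate. The adjusted between-arm difference is reported with its two-sided 95% CI. UACR and other skewed markers such as hsCRP and IL-6 are log-transformed (outcome and baseline) and reported as ratios of geometric means. Within-arm changes are descriptive only, using paired summaries.

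Then either name UACR as the lead primary outcome, or state that the primary outcomes are reported as estimates with CIs and without a multiplicity claim.

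The essential step is naming the between-arm contrast; the covariate and the log scale are cheap additions. The cost is one degree of freedom (38 to 37 with 40 patients) and a ratio-scale result for log-transformed outcomes. It runs in SPSS. STUDY PROTOCOL already plans blood sampling at baseline and study end, which covers the blood outcomes.

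Side note, not part of the point: confirm that UACR is measured at baseline and week 12, and that the UPCI line in the Revised Budget (96 tests = 48 × 2) refers to it. The content of the flowchart and Appendix A is not visible in the text reviewed and may already say so, so no omission is claimed.

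### The planned Pearson correlations of changes give randomised arm no role; if the arms are pooled, a diet effect on both variables would by itself produce a correlation.

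*Combined protocol and SAP*

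**What the plan says.** Objective 3 reads "To determine the associations between renal outcome and metabolic parameters in patients with DKD who received LCBD and standard therapy". Both arms are therefore in scope, but the wording does not say whether one coefficient is wanted or one per arm.

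The method is a single sentence in the Statistical Analysis section: a Pearson's "correlation analysis would be carried out to determine the correlation of the changes of proteinuria, creatinine, weight loss, and other variables". It mentions no arm term, stratification, partial correlation or regression. A broken sentence fragment follows it, so some wording on scope may be lost or misplaced.

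The Hypotheses section expects the diet to act on both sides of this correlation. On the renal side: "LCBD reduces proteinuria and improves renal function compared to standard treatment in patients with DKD". On the metabolic side: "LCBD causes significant weight loss and improvement in other metabolic parameters compared to standard treatment in patients with DKD". Neither hypothesis comes with an effect size or a standard deviation.

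On numbers, the Sample Size Calculation section says "This will be a pilot study involving 20 patients per arm" and, allowing for "20% dropout, we would be recruiting 24 patients per arm".

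**The concern.** If the diet lowers both weight and UACR, patients in the LCBD arm tend to have larger falls in both, and patients in the control arm smaller falls in both. A scatter plot over all patients then shows two clusters displaced along a diagonal. A correlation through both clusters is non-zero even if, within each arm, a patient's weight loss says nothing about that patient's change in UACR.

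A significant coefficient would then partly or wholly repeat what objectives 1 and 2 already report, namely that the arms differ. The risk of misreading is realistic, because the background section offers weight loss as one possible explanation for the renal effects of newer diabetes drugs. A pooled weight-UACR correlation would readily be taken as support for that idea. The problem grows as the diet works better, which is the outcome the trial hopes for.

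**Working it through.** **The plan's own figure.** 20 per arm × 1.20 = 24 per arm, as stated. Dividing instead by the completion rate gives 20 / 0.80 = 25. The difference has no bearing here, and the check uses the 20 evaluable patients per arm. No sample-size figure is given for the correlation analysis.

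**Inputs.**
- From the Sample Size Calculation section: 20 per arm, 40 in total, equal arms.
- Assumed, because the documents are silent: a two-sided 5% test, and arm effects d1 (weight change) and d2 (UACR change) in within-arm SD units.
- Set by construction: zero correlation within each arm.

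**Formula.** With equal arms and no within-arm association, the covariance of the two changes over all patients comes only from the arm means and equals d1·d2/4. The variances are 1 + d1²/4 and 1 + d2²/4. So

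r = (d1·d2/4) / √[(1 + d1²/4)(1 + d2²/4)].

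Example with 0.91 on both: 0.91²/4 = 0.207, so r = 0.207/1.207 = 0.17.
Example with 2 and 0.91: 1.82/4 = 0.455, and √(2 × 1.207) = 1.554, so r = 0.455/1.554 = 0.29.

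With n = 40, significance needs |r| above 0.312.

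**Rate of a significant result.** Simulated trials with 20 per arm (40,000 per scenario in the main runs):

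| Weight effect (SD) | UACR effect (SD) | Induced r | Pooled Pearson significant |
|---|---|---|---|
| 0 | 0 | 0.00 | about 5% |
| 1 | 0 | 0.00 | about 5% |
| 2 | 0 | 0.00 | about 5% |
| 0.3 | 0.3 | 0.02 | about 5% |
| 0.5 | 0.5 | 0.06 | about 6% |
| 0.8 | 0.8 | 0.14 | about 14% |
| 1.5 | 0.5 | 0.15 | about 15% |
| 0.91 | 0.91 | 0.17 | about 19% |
| 2 | 0.5 | 0.17 | about 19% |
| 1 | 1 | 0.20 | about 24% |
| 1.5 | 0.91 | 0.25 | about 35% |
| 2 | 0.91 | 0.29 | about 47% |

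Wherever the partial correlation given arm was run alongside, it was significant in about 5% of trials, whatever the arm effects. The value 0.91 SD is not an expected effect in this trial. It is the difference that 20 per arm detects with about 80% power, and serves only as a reference point.

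**Price of adjusting.** By the Fisher z approximation, the correlation detectable with 80% power is tanh[(1.96 + 0.84)/√(n − 3 − k)], where k is the number of variables adjusted for:
- pooled, n = 40, k = 0: tanh(2.80/√37) = 0.43
- adjusted for arm, n = 40, k = 1: tanh(2.80/√36) = 0.44
- one arm alone, n = 20, k = 0: tanh(2.80/√17) = 0.59

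**The case against.** The strongest reply is that the plan never says the arms are pooled. Objective 3 fits one coefficient per arm as well as one overall, and separate by-arm correlations would not have this defect. That stands: a reader might infer that pooling is stated, and it is not. What the text supports is that arm has no specified role and that a single unadjusted analysis is the natural reading. The need for a clarifying sentence is the same either way.

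Second, the artefact needs a diet effect on both variables. If either is zero, or both are about 0.3 SD, the pooled test keeps its level. This also stands. A reader might infer from the upper rows of the table that serious distortion is certain; the documents give no effect sizes that would show it. The two effects need not both be large, however: 2 SD on weight with 0.5 SD on UACR already gives about 19%.

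Third, objective 3 speaks only of associations. When both arm effects are real, the overall correlation truly is non-zero, and rejecting zero is correct for that quantity. The percentages are errors only if the target is a link within arms. That is fair, and a pooled coefficient is legitimate description if labelled as containing the arm difference. The plan has no such label. It also plans no mediation claim, so mediation is something a reader of the results might infer, not something the protocol asserts.

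Finally, this is the third objective of a pilot study and leaves the between-arm comparisons untouched. That limits the weight of the point but does not remove it.

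**Conclusion.** The point holds as a gap in specification. The plan names a plain Pearson correlation of changes, gives arm no role, and applies it to an objective covering both arms. If the arms are pooled and the diet moves both variables as hypothesised, the coefficient cannot distinguish a patient-level association from the difference between arms.

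The size depends on effects that the documents do not give. Over the assumed range, with 20 per arm, zero within-arm correlation and a two-sided 5% test, the pooled correlation is significant in about 5% to about 47% of trials, against about 5% for the partial correlation given arm. The documents do not support saying that the plan prescribes pooling, or that the distortion is bound to be large.

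**What to change.** In the Statistical Analysis section, replace the plain Pearson correlation with a partial correlation of the changes adjusted for randomised arm. A regression of renal change on metabolic change with an arm term serves the same purpose. Adding further covariates, such as baseline UACR, would make it a different analysis and is a separate decision.

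Show the within-arm correlations with confidence intervals as description only, since 20 patients per arm is too few to rest the objective on. State that the result will be reported as an association and not as mediation.

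The cost is one sentence and one degree of freedom: the detectable correlation at 80% power moves from about 0.43 to about 0.44. SPSS, the package named in the plan, offers partial correlation. No extra patients or measurements are needed.
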